1.0 Study Endpoints (if applicable)

- Clinical assessment response after 4, 8 or 12 weeks. This will be assessed by a blinded study team member comparing clinical photographs and dermascopic images.
 - Clinical photographs measured by no response, partial resolution, complete resolution.
 - Dermoscopy images: no response, partial resolution, complete resolution using the guidelines below that indicate the presence of wart or mollusum.
 - Molluscum: Visualization of a central umbilication with polylobular, white to yellow, amorphous structures is typical. A peripheral crown of radiating or punctiform vessels is also present.
 - Wart: grouped papillae, with dotted or loop vessels, and/or hemorrhagic points and lines often surrounded by a whitish halo
- Visual analogue scale for experimental treatment and control treatment
 - The visual analogue scale (VAS) is a validated subjective measurement of pain experienced by the patient. It consists of visual-numeric scale, numbered from 0-10. (0) indicate absence of pain or "no pain at all", while (10) indicates severe pain or "worst imaginable pain". This is supplemented by six faces with different expressions, ranging from happy to extremely upset. Each facial expression is assigned a numerical scale from 0 to 10.
- Evaluation of tolerability included assessment of dry ness, peeling, scaling, erythema, edema, stinging, burning sensation, itching, scaring and dyspigmentation. They will be assessed by means of a standardized grading scale (0 = absent; 1 = mild; 2 = moderate; 3 = severe)

5.0 Inclusion and Exclusion Criteria/ Study Population

Inclusion Criteria

- All patients from 4-21 years old with at least 1 lesion of vercurra or molluscum.
- Willingness of the participant and their guardian to provide consent when applicable.

Exclusion Criteria

- Unwillingness to participate in the study
- Received any treatment on the lesion in the past month determined by review of their medical record
- Immunodeficiency determined by review of their medical record.
- Adverse response to prior treatments determined by review of medical record.
- Signs of self-resolution determined by study team members.
- Conditions that lead to excessive scarring determined by study team members.
- Face and genital lesions determined by study team members.

6.0 Number of Subjects

Total of 150 would be required (half control, half NTP) to achieve 80% power with an alpha of

.05.

Calculation:

- Assumption for Probabilities for the Null hypotheses is P1=P2=P3=1, hence P1 = .333333, P2 = .333333, P3 = .333333 and P1+P2+P3 = 1.0 or that each proportion has an equal chance.
- Assumption for Probabilities for Alternative Hypothesis is taken from Provided NTP paper where P1=9/17 (Full Resolution = .53), P2=3/17=.18 (Some Improvement), and P3=5/17=.29 (no improvement).

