1.0 Objectives / Specific Aims

- Objective: Study the safety and efficacy of uniform nonequilibrium, nonthermal atmospheric pressure plasma (NTAP)/cold atmospheric plasma device (CAP) in the treatment of molluscum contagiosum and vercurra (warts) in children 4-21 years.
- Aim:
 - Measure the changes in size, pain and appearance of verrucae and molluscum after 4, 8 and 12 weeks.
 - Evaluate the safety profile and patient tolerability of the treatment by analyzing potential side effects and pain levels, or lack thereof, with each treatment.
- Hypothesis: NTAP will be an equally efficient and painless alternative to cryotherapy for the treatment of molluscum and warts.

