3.0 Intervention to be studied (if applicable)

We will utilize a floating electrode-dielectric barrier device (FE-DBD) Cold atmospheric plasma (CAP) device on molluscum and warts in children and adolescents 4-21 years (Figure 1). Children and adolescents are targeted because they are the population most affected by painful standard of care therapy. The study will continue until at least 68 warts and 68 molluscum are treated. Each patient will not have more lesions treated than SOC recommendations. Half the lesions will be treated with plasma and the other half with standard of care being cryotherapy for warts and cantharidin for molluscum. A single patient must have minimum of 1 clinically diagnosed lesion treated and maximum of 20 treated. Lesions with a clinical impression of warts or molluscum will be selected. Selection of treatment type (control vs NTAP) will be randomly selected. Lesions

Page 3 of 13

The treatment device in this study generates cold atmospheric plasma. Cold atmospheric plasma has certain properties of plasma, such as ionized gas molecules. To create plasma, a pulse generator supplying 20-kV pulse of 20-ns pulse width at 200 Hz (FPG10-01NM10, FID GmbH, Burbach, Germany) to a 5-mm diameter quartz-covered copper electrode of 10-cm length and 1-mm quartz thickness (5). These nanosecond pulse parameters were chosen to provide sufficient treatment dose at the high level of plasma uniformity required to avoid any tissue damage. We treated the lesions for approximately 1 to 2 minutes each, moving the electrode gently over the treatment area.

After the study treatments are completed, we will analyze the data to see if the treatment was safe and effective.

Non-significant risk device statement (6-19) (Figure 1)

- We are proposing a clinical trial floating electrode-dielectric barrier device (FE-DBD) a Cold Atmospheric Plasma (CAP) device.
- While novel to the medical field and especially to dermatology, there are already a number of publications regarding its use on human skin in adults (20-26) and children (29).
- CAP devices utilize noble gases (such as helium) to deliver plasma state matter to the skin. As
 its name implies, the generated plasma stream is of near skin temperature and it exists on
 normal atmospheric pressure. During the generation of the plasma there is no electric contact
 with the patient. The treatment does not increase skin surface temperature and the used helium

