10.0 Study Design / Methods

- A chart review of patient the patient's medical record will be completed and the following information will be collected for research purposes: DOB, demographics, contact information and diagnosis.
- Skin irritants, emollients, topical medications and other topical products cannot be applied to the study area 4 weeks prior to the start of the study and throughout the duration of the study. Details of what can and cannot be used can be discussed any time.
- During a clinical care visit, if a patient is eligible and agrees to participate, lesions will be selected by the dermatologist prior to procedure. The lesions will be marked randomly for a certain treatment regimen and photographs will be taken before each treatment and after completion of the study. Identifiers will be covered to protect identity. All images will be saved on a MUSC network secure box drive using a subject study number.
- The number of lesions treated will not exceed SOC recommendations. They will be determined by provider assessment and anatomical location.
- Participants with one lesion will receive either NTAP or standard of care (SOC). SOC is

Page 8 of 13

cryotherapy for warts and cantharidin for molluscum. Participants with greater than 2 lesions will receive equal treatment of NTAP and SOC. The number of lesions treated will be based off the providers assessment and anatomical location. Treatment of a single lesion or an odd number of multiple lesions will be based off a randomized list.

- All SOC lesions will be treated first to reduce the number of patients not wanting return to the more painful modality.
- All people in the room will be provided eye shields that must be worn during treatment. The patient will be placed in a comfortable position before the lesion is cleaned with alcohol.
- Each lesion will be treated for 1-2 minutes. Total treatment duration will be no longer than 20 minutes.
- The interval between treatment groups will about 1 minute.
- There will be a follow-up phone call a week after treatment to check on resolution and report any adverse events. If an adverse event is reported the study team members will access if the patient needs to be seen by a provider that day.

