- Patient will return to the office for a 4-week standard of care follow-up. Study cessation or additional treatment will be determined by the provider assessment of lesion clearance. If lesion persist another treatment will occur. No greater than 3 treatments will be performed.
- This study will be single blinded, meaning the study team member accessing the results will
 not know which lesions were treated with what therapy. Assessment of clearance will be based
 off of clinical examination and images. The team will record any additional clinical feature
 that may arise during the analyses.

11. Data Management

- Continuous data will be summarized using descriptive statistics (number of values, means, standard deviation, median, minimum and maximum). Categorical data will be summarized using frequency tables (frequencies and percent).
- Chi-square analysis comparing the proportions of successes (equal chance outcomes).
- Coded dermoscopic and clinical photographs may be obtained for further analyses after each visit. Files with patient images will be stored in a secure departmental drive that will only be accessible to study team members by their unique MUSC ID and password.
- All subject medical record information and data collection will be coded and stored on an MUSC Box drive only accessible to study team members and will be protected by two-factor authentication. The linking document between ID and PHI will be maintained separately from the study data in a separate encrypted folder.

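### The 80% power claimed for 150 in Section 6.0 cannot be shown to be power for plasma versus standard of care: no standard-of-care rate is given and the basis of 150 is undocumented

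*Combined protocol and SAP*

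**What the plan says.** Section 6.0 (Number of Subjects) gives the size: "Total of 150 would be required (half control, half NTP) to achieve 80% power with an alpha of" .05. It does not say whether the test is one- or two-sided. The null hypothesis sets each of three outcome probabilities to .333333, with the gloss "P1+P2+P3 = 1.0 or that each proportion has an equal chance". The alternative comes from one plasma paper: "P1=9/17 (Full Resolution = .53), P2=3/17=.18 (Some Improvement), and P3=5/17=.29 (no improvement").

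Section 11 (Data Management) names the test: "Chi-square analysis comparing the proportions of successes (equal chance outcomes").

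Section 3.0 describes the comparison: "Half the lesions will be treated with plasma and the other half with standard of care being cryotherapy for warts and cantharidin for molluscum". It sets a minimum of 68 warts and 68 molluscum lesions, and adds: "A single patient must have minimum of 1 clinically diagnosed lesion treated and maximum of 20 treated". Section 10.0 splits treatments within a child: "Participants with greater than 2 lesions will receive equal treatment of NTAP and SOC". The hypothesis in Section 1.0 is that "NTAP will be an equally efficient and painless alternative to cryotherapy for the treatment of molluscum and warts".

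**The concern.** Power for a two-arm comparison needs an assumption for each arm. Section 6.0 describes only the plasma arm. Its null says that three outcome categories are equally likely, which is not the statement that the two treatments work equally well. Two equally effective treatments could both depart from one third per category, so rejecting that null says nothing about the comparator.

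A reader will nevertheless take 80% as the chance of detecting a difference between plasma and standard of care. That chance depends on a rate the plan does not state. If the plan's own hypothesis of equal efficacy is true, a two-sided test for a difference rejects only about 5% of the time. A non-significant result could then be read as confirming equal efficacy when the estimate is too imprecise to show it.

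The unit is a second gap. The heading of Section 6.0 points to subjects, while Section 3.0 counts lesions and arrives at a different number.

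**Working it through.** **Inputs from the documents**
- Section 6.0: total 150, so 75 per arm if halved; power 80%; alpha .05, sidedness not stated; null 1/3, 1/3, 1/3; plasma results 9/17, 3/17, 5/17, printed as .53, .18, .29.
- Study Endpoints: three response levels, so 2 degrees of freedom.
- Section 3.0: 68 + 68 = 136 lesions; 68/2 = 34 per treatment per disease.

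Any standard-of-care rate used below is an assumption. Observations are treated as independent throughout.

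**1. Goodness of fit, the test that matches the stated null.** The noncentrality for 80% power at alpha .05 with 2 df is 9.63.

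w² = 3 × [(9/17 − 1/3)² + (3/17 − 1/3)² + (5/17 − 1/3)²] = 3 × (0.0384 + 0.0246 + 0.0015) = 0.1938

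N = 9.63/0.1938 = 49.7 (50.1 with the printed decimals), so about 50 in one group, or 100 if doubled for two arms. Power is 94% at 75 and 99.9% at 150. This gives neither 150 nor 80%.

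**2. 2x3 chi-square, assuming one third per category for control.** The category averages of the two arms are 0.4314, 0.2549 and 0.3137.

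w² = Σ[(p − 1/3)/2]²/average = 0.0223 + 0.0241 + 0.0012 = 0.0476

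N = 202.2, so 203 (205.8, so 206, with the printed decimals). Power at 150 is 0.665 (0.657).

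**3. 2x2 on full resolution, assuming one third for control.** With p̄ the mean of the two rates:

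n per arm = [zα√(2p̄(1 − p̄)) + 0.842√(p1(1 − p1) + p2(1 − p2))]² / (p1 − p2)²

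| Rates | Test at .05 | n per arm | Total |
|---|---|---|---|
| 9/17 v 1/3 | two-sided | 98.96, so 99 | 198 |
| .53 v .33 | two-sided | 95.0005, so 96 | 192 |
| 9/17 v 1/3 | one-sided | 77.8, so 78 | 156 |
| .53 v .33 | one-sided | 74.7, so 75 | 150 |

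The last row is (1.645√0.4902 + 0.842√0.4702)²/0.04 = 74.7. It matches the plan's figure, with power 0.801 at 75 per arm. Using the printed .333333 with .53 gives 78 per arm. A two-sided test at 75 per arm has power 0.700 for .53 v .33 and 0.682 for 9/17 v 1/3.

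**4. Dependence on the missing rate (illustration).** Plasma at 9/17, two-sided .05, 75 per arm:

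| Assumed standard-of-care clearance | Power |
|---|---|
| 30% | 82% |
| 33.3% | 68% |
| 40% | 35% |
| equal to plasma | about 5% |
| 60% | 14% |
| 75% | 81% |

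Power reaches 80% only when the assumed rate lies outside about 31% to 75%. At 34 per arm, the Section 3.0 minimum for one disease, power against an assumed 33.3% is about 37%.

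**5. Precision if the arms are equal at 9/17.** The 95% half-width is 1.96√(2 × (9/17)(8/17)/n):
- n = 75: 0.160, about 16 points
- n = 34: 0.237, about 24 points

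**The case against.** The strongest reply is that Section 6.0 does contain a two-arm calculation, only tersely written. It refers to both arms, and Section 11 refers to proportions of successes. If one third is taken as the control success rate, a one-sided comparison of .53 with .33 gives exactly 150. The unpooled one-sided formula on 9/17 and 1/3 comes close, at 152. A reader might therefore infer from this review that 150 is miscalculated, or that 80% is definitely not the two-arm power. The documents do not support that stronger reading, because such a route exists. It does require a one-sided test the plan does not state, a 33% control rate it neither states nor sources, rounding of its own .333333, and collapsing three categories to two. It would also test superiority over that rate, whereas Section 1.0 hypothesises equal efficacy.

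A reader might also infer that Section 11 plans no comparison between treatments. That goes too far. The wording can mean comparing success between treatments under a null of equal chance, or testing three equally likely outcomes. It needs to be made explicit.

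Nor should it be inferred that several lesions per child necessarily reduce precision. Correlation among lesions given the same treatment widens the interval, but splitting treatments within a child can narrow it. The plan gives no correlations, so neither direction nor size can be fixed. For the same reason, the calculations for 75 per arm describe one scenario: 75 independent observations per arm with both diseases pooled. Whether the 17 in the source series counts patients or lesions cannot be checked either.

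**Conclusion.** The point stands as a documentation and specification failure. On the inputs printed in Section 6.0, neither version of the chi-square named in Section 11 yields 150 at 80% power: one needs about 50, the other 203 to 206. The one route that reproduces 150 rests on two unstated assumptions, and the same 75 per arm has about 70% power once the test is two-sided (68% for 9/17 v 1/3). With no standard-of-care rate in the documents, no single corrected power can be given.

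The unit remains open. The 150 under a heading about subjects is not reconciled with the 136-lesion minimum in Section 3.0, and neither number allows for up to 20 lesions from one child. This should be corrected before analysis because it determines what the trial can conclude, in particular whether a non-significant result may be presented as equal efficacy.

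**What to change.** **Section 6.0**
- Remove the equal-thirds null as the basis of the two-arm size.
- State whether 150 counts children or lesions, and reconcile it with the 136 lesions in Section 3.0.
- State an assumed standard-of-care response rate with its source, and the sidedness of the test.
- Replace the 80% claim with the power, or the expected 95% confidence-interval width, for plasma versus standard of care under that assumption, allowing for lesions within the same child.

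**Section 11**
- Replace the ambiguous equal-chance wording with an explicit between-treatment comparison of response that allows for lesions within the same child.
- Report the plasma minus standard-of-care difference with a 95% confidence interval.
- State that a non-significant test will not be read as equal efficacy.

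**Cost.** Wording in two sections, an external source for the control rate, and a less favourable power statement. No extra enrolment is requested, though the sponsor may wish to revisit the size once the power is restated. A formal equal-efficacy test is not requested; it would need a margin that the plan does not give.

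### The single 80% power figure for a total of 150 does not carry over to two disease comparisons of about 34 v 34 lesions each

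*Combined protocol and SAP*

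**What the plan says.** Section 6.0 (Number of Subjects) gives one sample size and one power: "Total of 150 would be required (half control, half NTP) to achieve 80% power with an alpha of" .05. The null is "P1 = .333333, P2 = .333333, P3 = .333333 and P1+P2+P3 = 1.0 or that each proportion has an equal chance". The alternative, taken from a published plasma paper, is "P1=9/17 (Full Resolution = .53), P2=3/17=.18 (Some Improvement), and P3=5/17=.29 (no improvement". There is one set of proportions and no split by disease.

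Section 3.0 sets the stopping rule for enrolment by disease and in lesions: "The study will continue until at least 68 warts and 68 molluscum are treated". Half of the lesions receive plasma and half the control, with "standard of care being cryotherapy for warts and cantharidin for molluscum". The hypothesis in Section 1.0 covers both diseases: "NTAP will be an equally efficient and painless alternative to cryotherapy for the treatment of molluscum and warts".

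Section 11 (Data Management) names a chi-square analysis of the proportions of successes. It does not say whether warts and molluscum are pooled or tested separately. No section gives a power for either disease.

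**The concern.** Sections 3.0 and 6.0 describe different things. Section 6.0 sizes one comparison. Section 3.0 creates two, in different diseases and against different controls, each with less than half of the quoted total at its floor. A test that merges them mixes two diseases and two comparators, so it cannot say whether NTAP performs like cryotherapy in warts or like cantharidin in molluscum. Section 2.0 says that efficacy in molluscum is untested, so that disease needs its own estimate.

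The hypothesis adds to the problem. Because it claims that NTAP is as efficient as the control, a non-significant difference in one disease could be taken as support when it may only reflect a small sample.

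**Working it through.** **Inputs.** From Section 6.0: total 150, power 80%, alpha .05, null (1/3, 1/3, 1/3), alternative (9/17, 3/17, 5/17). From Section 3.0: floor of 68 lesions per disease, half per treatment, so 34 v 34; both diseases together 68 + 68 = 136. The test is the chi-square of Section 11, with three grades and therefore 2 df.

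**Formula.** Power = P(noncentral chi-square with 2 df and noncentrality λ exceeds −2 ln 0.05 = 5.99), where λ = N·w².

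**1. Does 150 reproduce?**

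- *One-sample test against equal thirds.* w² = 3 × (81 + 9 + 25)/289 − 1 = 56/289 = 0.1938. 80% power needs 50 lesions in one group (100 if doubled); 150 would give 99.9%.
- *Two-arm 2×3 test, control assumed at one third per grade.* In units of 1/51, NTAP is (27, 9, 15), control is (17, 17, 17), and their average is (22, 13, 16). Then w² = (25/22 + 16/13 + 1/16)/51 = 2.4296/51 = 0.04764. 80% power needs 203 in total; at 150, λ = 7.15 and power is 66.5%.
- *Full resolution only, 9/17 v 1/3.* The two-sided test needs 198. The one-sided test needs 156 and has 78.7% at 150, which is close, but it is not the three-category chi-square described.

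None of these gives 150. Power at the floor was therefore worked out in two ways.

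**2. Power of a two-arm chi-square.** Column A uses Section 6.0's proportions with control at equal thirds (λ = 0.04764 N). Column B takes 80% at 150 as given, which fixes λ = 9.635 at N = 150, and rescales (λ = 9.635 N/150).

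| Lesions in the comparison | A: λ, power | B: λ, power |
|---|---|---|
| 68 (one disease at the floor) | 3.24, 34.4% | 4.37, 44.9% |
| 75 (150 split evenly by disease) | 3.57, 37.6% | 4.82, 48.8% |
| 136 (both floors combined) | 6.48, 61.9% | 8.74, 75.7% |
| 150 | 7.15, 66.5% | 9.63, 80% |

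Simulation of case A at 34 v 34 gives 35.0%.

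**3. Other tests at the per-disease floor.** Two proportions on full resolution, 9/17 v 1/3: 36.9% two-sided, 49.5% one-sided. One-sample test against equal thirds: λ = 34 × 0.1938 = 6.59, power 62.7% on the 34 NTAP lesions. It reaches 91.2% only if all 68 lesions, controls included, enter the one-sample test.

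**The case against.** The strongest reply is that no single percentage is the power of this trial.

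- **The 45% is back-solved.** It belongs to whatever effect would give 80% at 150, not to the effect in Section 6.0. This stands, so 45% is given only as conditional.
- **The 34% borrows the null as a control rate.** Section 6.0 offers equal thirds as null probabilities and never as an expected cryotherapy or cantharidin outcome. This also stands, and the assumption has to travel with the figure.
- **The wording of Sections 6.0 and 11 fits a one-sample test against equal chance.** That test has about 63% power on 34 NTAP lesions. A reader might infer that each disease comparison is more likely than not to miss the assumed effect; on this literal reading that is not so. But the one-sample test does not compare NTAP with control, which the randomised allocation and the hypothesis call for.
- **The units differ.** The 150 stands under a heading about subjects, whereas 68 counts lesions, and one patient may contribute 1 to 20. If 150 means patients, lesion numbers could be well above the floor. The 68 is also a minimum.
- **Lesions are clustered, and patients with several receive both treatments.** Correlation could move power either way, and no intraclass correlation is given.
- **Testing by disease is an inference.** The plan is silent, and that silence is part of the problem. Pooling does not rescue the figure: at 136 lesions neither column reaches 80%.

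**Conclusion.** The concern holds in conditional form. Section 6.0's 80% is not the power of either disease comparison at the size that Section 3.0 allows. A two-arm chi-square (2 df, alpha .05) at 34 v 34 has about 34% power with Section 6.0's proportions and control at equal thirds, or about 45% if 80% at 150 is taken as given. At the combined floor of 136 it has about 62% or 76%. These figures assume that 150 counts lesions, that lesions are independent, and that enrolment stops at the floor.

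Two further inferences should be avoided. A reader might take 45% as the power of Section 6.0's stated effect; it is not, because 150 does not follow from those proportions. A reader might also conclude that 80% is correct for warts and molluscum pooled. The documents do not say so, and with Section 6.0's proportions a pooled two-arm test of 150 has 66.5%.

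**What to change.** **Section 6.0.** State whether 150 means lesions or subjects, and reconcile it with 68 + 68 = 136. Replace the single 80% with the recomputed power of each disease comparison at 34 v 34, giving the control rates assumed for cryotherapy and for cantharidin. Do not restate 80% as the power of a pooled comparison.

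**Section 11.** Compare NTAP with standard of care separately for warts (v cryotherapy) and molluscum (v cantharidin), each with a response difference and 95% confidence interval. Give any combined result as a disease-stratified (Cochran-Mantel-Haenszel) summary. State that a non-significant difference will not be read as showing equal efficacy.

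**Cost.** Wording in two sections and two disease-specific tables. The stated power becomes less favourable. No added enrolment or procedures.

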Multiple modes of NTAP, also known as cold atmospheric plasma (CAP), have been employed in dermatologic clinical studies such as wound healing, onychomycosis, actinic keratosis and viral warts (28). Friedman's case series on warts proved it safety and efficacy in children, reporting no adverse events (blistering, scarring, significant pigmentary alteration or persistent nail changes) or pain reported in treatment (29). A proof-of-concept study on warts in children demonstrated efficacy and exceptional tolerability when treated with plasma as a result of its intracellular calcium influx and viral replication inhibiting effects. In actinic keratosis they had a 70% improvement rate with no discomfort during or after treatment. Onychomycosis had a 50% clinical and 15% mycological cure rate in 13 patients without any side effects. And wound healing of chronic ulcers had decreased bacterial as expected from well-documented inhibitory effects on bacteria and also superior wound healing rates compared to wound care alone. Moreover, it has been shown to be safe and successful in proof-of concept studies exploring its application in the treatment of Verruca vulgaris. Its efficacy in molluscum has not yet been tested.

Given NTAP's outstanding safety profile and painless application (5), its prior proof of concept success in treating common verrucae, and the similarity between verrucae and molluscum, we propose to use NTAP to treat these conditions and expand upon the existing research literature.

If the NTAP device is shown to be a successful, efficacious and painless treatment option for children and adolescents with verrucae and molluscum, this would be a revolutionary and environmentally friendly approach to two of the most common viral infections and chief complaints found during dermatology visits in this age group. The non-toxic, chemical free, waste free, multi-year device results in a significant reduction of effluents, which is beneficial from an economic but also an environmental viewpoint (30).

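### Section 6.0 gives one 80% power figure for a two-disease trial, from rates whose disease is not named; at the plan's own rates neither disease has 80% power at its minimum of 68 lesions

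*Combined protocol and SAP*

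**What the plan says.** Section 6.0 (Number of Subjects) makes one power statement for the whole trial: "Total of 150 would be required (half control, half NTP) to achieve 80% power with an alpha of" 0.05. The null puts one third in each response category: "hence P1 = .333333, P2 = .333333, P3 = .333333 and P1+P2+P3 = 1.0". The alternative is "taken from Provided NTP paper where P1=9/17 (Full Resolution = .53), P2=3/17=.18 (Some Improvement", with the remainder given as "P3=5/17=.29 (no improvement". No reference number, disease or population is attached to these rates, although the protocol carries a 30-item reference list.

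Section 3.0 sets the recruitment target by disease: at least 68 warts and at least 68 molluscum lesions, half treated with plasma and half with standard of care. Section 11 (Data Management) plans a chi-square analysis against equal-chance outcomes.

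Section 2.0 (Background) gives a plasma response figure for actinic keratosis, "In actinic keratosis they had a 70% improvement rate with no discomfort during or after treatment", and cure rates for onychomycosis (50% clinical and 15% mycological, in 13 patients). For warts it reports success, including in children, but gives no rate. For molluscum it says "Its efficacy in molluscum has not yet been tested".

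**The concern.** The assumed response rates determine the power claim, and here they cannot be traced. One three-category split, from 17 observations of unstated origin, stands for two diseases with different standard treatments. For molluscum, half of the minimum lesion count, no observed plasma rate can lie behind it, and Section 6.0 does not say that the rate is an assumption.

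The recruitment target is set by disease but the power is not. A reader would take the 80% as the chance of detecting the assumed effect in warts and in molluscum. If the true per-disease power is much lower, a null result in one disease, molluscum especially, would be read as evidence of no effect when the design had little chance of showing one.

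**Working it through.** **Inputs.** From Section 6.0: alternative 9/17, 3/17, 5/17; null 1/3 each; alpha 0.05; stated total 150 for 80% power. From Section 3.0: at least 68 lesions per disease, half plasma, so 34 plasma and 34 control lesions per disease. Assumption: lesions are independent. All power figures use the noncentral chi-square with 2 degrees of freedom (critical value 5.99) and noncentrality λ = n·w².

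**1. What the source can be.** Full plus partial response is (9 + 3)/17 = 12/17 = 70.6%. Among the plasma response figures in Section 2.0, only the 70% for actinic keratosis agrees. That figure has no denominator and no full/partial split, so only the sum can be compared. The exact 95% interval for 9/17 is 27.8% to 77.0%, so the full-resolution rate is loosely known even in its own disease.

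**2. The plan's own figure.**

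- *Goodness of fit against one third each.* w² = Σ(p − 1/3)²/(1/3) = 3·(81 + 9 + 25)/289 − 1 = 56/289 = 0.1938. This needs n = 50 for 80% power. At n = 75 the power is 93.7%, and at n = 150 it is 99.9%.
- *Two-arm 2x3 chi-square, 1:1, control at one third each.* The arm averages are 0.4314, 0.2549 and 0.3137. w² = Σ d²/(4·average) with d = 0.1961, −0.1569, −0.0392, which gives 0.0223 + 0.0241 + 0.0012 = 0.0476. This needs 203 in total. At N = 150, λ = 7.15 and power is 66.5%. At N = 136 (68 + 68), power is 61.9%.
- *Full resolution only, 9/17 against 1/3.* Two-sided tests need 194 to 218 in total, depending on the formula. A one-sided test needs 156 (pooled variance) or 152 (unpooled).

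Neither three-category test reproduces 150 at 80%. Only a one-sided, two-category comparison that the plan does not describe comes close.

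**3. Power per disease at the planned minimum, with the plan's own rates.**

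- Goodness of fit on 34 plasma lesions: λ = 34 × 0.1938 = 6.59, power 62.7%. A simulation of the same test gave 63.1%.
- Two-arm 2x3 test on 68 lesions: λ = 68 × 0.0476 = 3.24, power 34.4%.

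**4. Sensitivity to the plasma rate.** The splits below (full/partial/none) are assumptions for illustration and are not taken from any wart or molluscum data. The null stays at one third each.

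| Assumed split | w², goodness of fit | Power, 34 plasma lesions | w², 2x3 | Power, 68 lesions |
|---|---|---|---|---|
| 60/15/25 | 0.335 | 87% | 0.0788 | 53% |
| 9/17, 3/17, 5/17 | 0.194 | 63% | 0.0476 | 34% |
| 50/20/30 | 0.140 | 48% | 0.0342 | 26% |
| 45/25/30 | 0.065 | 25% | 0.0155 | 14% |

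All four full-resolution rates lie inside the interval in step 1.

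**The case against.** A reader might infer from the 70.6% that the rates are the actinic keratosis result, and so that the power claim rests on a disease the trial does not treat. The documents do not support that. Three proportions cannot be matched to one percentage. Section 2.0 gives no rate at all for warts, so the absence of a matching wart figure is not evidence against a wart source. The agreement is a reason to ask, and no more.

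Section 2.0 also offers a rationale for carrying a wart rate over to molluscum: earlier success in common warts and the similarity of the two conditions. Lack of molluscum data is usual in a first study and is disclosed there. That stands, if the source is a wart paper. It makes the molluscum rate a reasoned assumption; it does not make the 80% apply to 34 plasma lesions.

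It can also be said that 150 at 80% fails to follow from the planned chi-square whatever the disease, that required sizes grow without limit as a split nears one third each, and that 68 per disease is a minimum. All three are true. The sensitivity table therefore illustrates the range and does not estimate the error. The 63% and 34% do not depend on it, since they use only the plan's own rates, null and lesion minimum. Finally, pooling the plasma lesions of both diseases (68) gives 91% by goodness of fit, but that answers a question about the two diseases combined and assumes that they respond alike.

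**Conclusion.** The point holds in this form. Section 6.0 does not identify the paper or disease behind its rates. They are not molluscum data, and whether they come from warts, actinic keratosis or something else cannot be settled from the documents.

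At the plan's own rates and at 68 lesions per disease, power in each disease is about 63% (goodness of fit, 34 plasma lesions) or about 34% (two-arm 2x3). The stated 80% is therefore not delivered in either disease at that size, although a higher plasma rate could reach it under the goodness-of-fit test. These figures rest on independent lesions, a 34/34 split, and the plan's one-third null, also used as the control distribution in the two-arm test. Whether one third is a suitable null or control rate is a separate question. No corrected sample size can be given, because the documents contain no wart, molluscum or control response rates.

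**What to change.** In Section 6.0, replace the single power statement with achieved power for warts and for molluscum separately, each at 68 lesions (34 per treatment), for the test that will be used. Show it over a range of plasma response splits labelled as assumptions, and state the null or control rate used. Name the paper and disease behind 9/17, 3/17, 5/17. If it is not a wart paper, base the wart rate on the paediatric wart case series already cited (reference 29), where that series reports a usable rate. Say plainly that the molluscum rate is an assumption, and whether it is borrowed from warts.

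The cost is a rewrite of one short section. Enrolment does not change. The downside is a stated power less favourable than 80%.
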